## **5.6 Blinding of Study Drug**

Not Applicable

## **5.7 Receiving, Storage, Dispensing and Return**

### **5.7.1 Receipt of Drug Supplies**

Drug to be delivered via Federal Express

Upon receipt of the study treatment supplies, an inventory must be performed and a drug receipt log filled out and signed by the person accepting the shipment. It is important that the designated study staff counts and verifies that the shipment contains all the items noted in the shipment inventory. Any damaged or unusable study drug in a given shipment (active drug or comparator) will be documented in the study files. The investigator must notify study sponsor of any damaged or unusable study treatments that were supplied to the investigator's site.

### **5.7.2 Storage**

The investigational drug will be in our locked cabinet and only the necessary vials will be withdrawn at the time of the study. They will be mixed by the administering physician in a sterile fashion.

### **5.7.3 Dispensing of Study Drug**

Regular study drug reconciliation will be performed to document drug assigned, drug consumed, and drug remaining. This reconciliation will be logged on the drug reconciliation form, and signed and dated by the study team.

### **5.7.4 Return or Destruction of Study Drug**

At the completion of the study, there will be a final reconciliation of drug shipped, drug consumed, and drug remaining. This reconciliation will be logged on the drug reconciliation form, signed and dated. Any discrepancies noted will be investigated, resolved, and documented.

## **6 Study Procedures**

Please refer to #3 above

## 7 Statistical Plan

### 7.1 Sample Size Determination

The total number of 0 patients will power this study adequately, however as we have extended the protocol to include the atrial fibrillation participants (and extra 60 pts) the difficulty in imaging the atria, coupled with the thin atrial walls, means that we expect a difference in DEMRI volume of 40 (+ or - 20) in participants with early disease and 60 (+ or - 20) in participants with advanced disease. Accordingly, 60 participants will be needed for the additional cohort. Our published pre-clinical study in 13 swine demonstrated the infarct volume percentage difference of 9% between MEMRI and DEMRI ( $p<0.001$ ). This difference will enable significant delineation of the changes in the peri-infarct viability between the cell therapy and control arms. The preliminary porcine data presented above demonstrated a mean of 100% increase in the CNR of the peri-infarct region and a mean of 50% decrease in the scar volume, suggesting robust MEMRI signal detection of stem cell engraftment and increased peri-infarct viability. Furthermore, the clinical trial in 6 ICM patients demonstrated significant difference in the infarct volume between MEMRI defect and DEMRI enhancement. This difference between MEMRI and DEMRI represents PIR assuring reliable detection of the PIR. Employing these data, in order to detect a mean difference of 20% in MEMRI signal of stem cell engraftment and MEMRI-DEMRI signal of peri-infarct viability with a standard deviation of 5%, the t-test sample size calculation in this study has 90% power at the alpha 0.05 significance level, assuming an equal variance between the two distributions.

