
over time, offering potential benefits over the nonspecific extracellular agents currently available for MRI or X-ray/CT procedures. This feature allows full use of the high resolution of MRI, since there is not a trade-off of high spatial resolution for temporal (first-pass) resolution. It is anticipated that the features offered by EVP1001-1 along with the high resolution, three-dimensional attributes of MRI will result in higher accuracy than is available with other current modalities in practice, including stress echocardiograms, cardiac MRI using gadolinium contrast and nuclear studies such as SPECT and PET. This will be evaluated in this study and serve as the basis for pivotal registration studies. All components of EVP1001-1 are USP and are approved for use as drugs in man, orally and/or intravenously. A summary of the Phase I safety and PK (pharmacokinetics) study are provided below. The Phase I study evaluated the safety and tolerance of EVP1001-1 in humans, with special emphasis on cardiovascular safety, and assessed its PK profile. Overall, EVP1001-1 was found to be safe at all doses. There were no serious adverse events (SAE) or any events requiring medical treatment. Of special importance, no signs of cardiac depression were reported. In addition, there was no observation of prolongation of the QTc or PR intervals or other ECG-changes that had previously been reported in animals for Mn. There were no changes in hematology, serum biochemistry (including liver function tests), coagulation parameters nor in temperature, respiratory rate or blood oxygen levels. Transient increases in HR and BP were seen. These, for the most part, reflected transient changes within the normal reference range. There was no obvious dose-relationship for these responses, although their duration and magnitude were greater for the 5-minute than for the 1-minute dose administrations. Other AEs were reported, almost all which were regarded as of mild or moderate intensity. Almost all events occurred during or immediately after dosing and resolved within minutes. Over 83% of the AEs occurred during dosing and over 93% occurred within one minute of dosing. Nearly one-third of all events resolved within one minute from dosing, over 80% within 5 minutes, and 94% resolved within 1 hour. The most frequent types of AEs were injection-associated discomforts (warmth, flushing, cold, pressure, injection site changes, increased HR/BP), gastrointestinal disturbances (discomforts, nausea, vomiting, diarrhea), lacrimation and headache. Although gastrointestinal disturbances, such as nausea and occasional vomiting, resolved rapidly without treatment, these bothersome events may be avoidable through the use of a standard anti-emetic. This proved to be beneficial in humans and also in high-dose animal studies. The PK profile reflected that known for Mn in humans (based on reported radiotracer Mn studies), with a primary blood half-life under 1 minute, and less than 1% of the dose remained in the blood by 30 minutes after dosing. The performance of EVP1001-1 was as expected based on information that was in the Investigators' Brochure. Lastly, please refer to US Patent #5,980,863 regarding further details of EVP1001-1 contrast ingredients.

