EVP is novel manganese (Mn)-based intravenous imaging agent being developed to enhance magnetic resonance imaging (MRI). While Mn has long been known to have desirable magnetic and kinetic properties for MRI, use in humans was not initially possible due to cardiovascular depression and electrocardiogram (ECG) changes, including prolongation of PR and QTc intervals, associated with intravenous administration. Chelation of Mn, as had been done with gadolinium for use with MRI, provided relevant safety, but sacrificed desirable magnetic and kinetic properties. EVP provides Mn in a form that maintains the desired magnetic and kinetic properties while overcoming the cardiovascular toxicity of Mn. EVP is taken up into heart cells (primarily via addition of calcium to avoid cardiotoxic effects; please refer to patent listed below). The potential to distinguish healthy heart tissue from unhealthy heart tissue based on a specific sustained pattern of enhancement provides a basis for evaluating the performance of EVP in heart patients. MRI offers benefits over other imaging technologies. Relative to radioactive nuclear imaging procedures, MRI is 3-dimensional, provides good soft tissue discrimination, and is of high spatial and temporal resolution. These features have been reported to identify smaller defects (e.g., sub-endocardial infarcts) and match angiographic results more closely than other modalities such as SPECT. It may be possible to enhance the utility of MRI for heart disease further through the use of an imaging agent that is specifically taken up into heart cells. EVP is the only cardiac-specific agent being developed for this purpose. Unlike nuclear perfusion agents, EVP is not radioactive and does not require special handling, shielding, transport or storage. In addition, the specific pattern of enhancement achieved in the heart muscle persists over time, offering potential benefits over the nonspecific extracellular agents currently available for MRI or X-ray/CT procedures. This feature allows full use of the high resolution of MRI since there is no trade-off of high spatial resolution for temporal (first-pass) resolution. It is anticipated that the features offered by EVP along with the high resolution, three dimensional attributes of MRI will result in higher accuracy than is available with other current modalities in practice, including stress echocardiograms, cardiac MRI using gadolinium contrast and nuclear studies such as SPECT and PET. This will be evaluated in this study and serve as the basis for pivotal studies for routine clinical application.

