#### **4.3 Subject Recruitment and Screening**

This is an open-label, baseline-controlled study to be conducted. Adult male or non-pregnant female patients who have been referred for evaluation of cardiomyopathy and atrial fibrillation and patients who have received stem cell therapy related to these indications will be recruited. An initial cohort study of 6 patients to conduct safety evaluation was conducted before proceeding with 120 additional patients. In the initial cohort, a patient was dosed based on the Phase 1 and 2 clinical trial data evaluation completed by Eagle Vision Pharmaceutical, Inc. Subjects were excluded if they had received an investigational device within 30 days prior to administration of EVP1001-1; had a history of drug abuse or alcoholism; were taking a digitalis preparation; had a history of torsades; had NYHA Grade IV heart failure; had abnormal liver function tests or a history of liver disease; had uncontrolled hypertension; had abnormal calcium, potassium or hemoglobin values at baseline; if they develop a cardiac arrhythmia prior to or during either of the exercise tests-- EVP1001-1 was not administered. The same parameters will apply to the new group of subjects.

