#### **5.3 Method for Assigning Subjects to Treatment Groups**

Not Applicable

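### Section 7.1 claims a cell-therapy versus control comparison that the protocol text does not set up; sections 1.1 and 1.4 also promise accuracy comparisons with modalities that are not scheduled

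*Combined protocol and SAP*

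**What the plan says.** Section 7.1 (Sample Size Determination) cites a published study in 13 swine in which infarct volume percentage differed by 9% between MEMRI and DEMRI, and continues: "This difference will enable significant delineation of the changes in the peri-infarct viability between the cell therapy and control arms". The same paragraph then states 90% power at alpha 0.05 for a mean difference of 20% with SD 5%, applied to a MEMRI signal of stem cell engraftment and a MEMRI-DEMRI signal of peri-infarct viability.

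On design, section 4.3 says: "This is an open-label, baseline-controlled study to be conducted". Its only provision for cell therapy is that "patients who have received stem cell therapy related to these indications will be recruited". Section 5.3, headed "Method for Assigning Subjects to Treatment Groups", reads "Not Applicable". Section 7.2 lists a Student's t-test of MEMRI against DEMRI, and a Pearson correlation of engraftment or viability with function or outcome.

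On accuracy, sections 1.1 and 1.4 expect EVP1001-1 MRI to be more accurate than current modalities, "including stress echocardiograms, cardiac MRI using gadolinium contrast and nuclear studies such as SPECT and PET". Section 1.1 adds: "This will be evaluated in this study and serve as the basis for pivotal registration studies". Section 1.4 has the parallel sentence: "This will be evaluated in this study and serve as the basis for pivotal studies for routine clinical application".

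**The concern.** A sample-size section tells the reader what the trial is able to conclude. This one says the trial can separate cell-treated patients from controls on change in peri-infarct viability. That would need defined groups, a size for each, a measurement before and after therapy (or a justified substitute), and a planned test. If these are absent, any contrast between recipients and other patients is unplanned and non-randomised, and the wording in 7.1 would lend it the standing of an arm comparison.

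The accuracy promise has a similar form. It names comparators and says that this study will supply the evidence for later pivotal work. If those comparators are not imaged, the study can say nothing about them.

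**Working it through.** **1. What an arm comparison needs, and what the text supplies**

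| Needed | Found in the protocol text |
|---|---|
| Cell-therapy and control arms | Not defined. Section 4.3 makes recipients one kind of eligible patient. |
| Number of recipients and controls | Not given. Totals are 50 (Study Summary, section 2), 60 (1.4, 7.3) or 120 (1.1, 4.3, 8.3.1), none split by cell exposure. |
| Change over time | Section 3.1 describes one MEMRI-then-DEMRI sequence, with no timing relative to cell therapy. |
| A matching objective | Specific Aims 1 and 2 (section 2) contain no cell-therapy comparison. |
| A between-group test | None in section 7.2. |

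**2. The stated 90% power**

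Inputs from 7.1: difference 20, SD 5, alpha 0.05 (taken as two-sided), power 90%, equal variances.

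n per group = 2(1.960 + 1.282)² × 5² / 20² = 2 × 10.51 × 0.0625 = 1.3, rounded up to 2.

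With the exact t distribution, 2 per group give 56% and 3 per group give 95%. Paired, taking 5 as the SD of within-patient differences, 3 patients give 91%. With totals of 50, 60 or 120 split equally, power is about 100%.

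The SD at which a difference of 20 has 90% power is 20 / [√(2/n) × 3.242]. This gives 21.8 for n = 25 per group, 23.9 for n = 30 and 33.8 for n = 60. The stated 90% therefore matches none of the document's totals, and 7.1 does not say which two distributions are compared. The patient total in the first sentence of 7.1 may have lost a digit in text extraction, and nothing here depends on it.

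**3. Whether the 9% can support an arm comparison**

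It is the difference between two imaging methods. An arm comparison needs the difference between treated and untreated subjects and the between-subject SD, and the 9% supplies neither. Section 7.1 also cites porcine cell-therapy data (CNR up by a mean of 100%, scar volume down by a mean of 50%). These do concern treatment, but they come without an SD or group sizes and do not fix an effect for patients.

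The following is illustration only. Assume a between-group difference of 9 points and an SD of either 11 (the ± value for DEMRI scar in the 6-patient study, read as an SD) or 20 (the value in 7.1 for the atrial cohort), and vary the share of recipients.

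Power = Φ(9 / [SD√(1/n₁ + 1/n₂)] − 1.960)

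For 5 recipients and 45 others with SD 11: 11 × √(1/5 + 1/45) = 5.185; 9/5.185 = 1.736; Φ(−0.224) = 0.411.

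| Total | Recipients | Power, SD 11 | Power, SD 20 |
|---|---|---|---|
| 50 | 10% | 0.411 | 0.157 |
| 50 | 20% | 0.638 | 0.246 |
| 50 | 50% | 0.825 | 0.356 |
| 60 | 10% | 0.477 | 0.180 |
| 60 | 50% | 0.887 | 0.414 |
| 120 | 10% | 0.767 | 0.315 |
| 120 | 50% | 0.994 | 0.693 |

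The spread from 0.157 to 0.994 shows that the answer is set by quantities the plan does not state.

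**4. Comparator modalities**

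| Named in 1.1 and 1.4 | Scheduled in 3.1 | Reference in 3.2 |
|---|---|---|
| Stress echo | No | No (echo is named, not stress echo) |
| Gadolinium MRI | Yes | Yes |
| SPECT | No | No |
| PET | No | No |

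Three of the four are neither scheduled nor used as a reference. The fourth is performed, but it is itself part of the reference, so higher accuracy than gadolinium MRI cannot be shown against that reference alone.

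**The case against.** The strongest reply is that the operative plan is sound and only the prose overreaches. Section 7.2 has no between-group test, so a treatment claim would need an analysis nobody has planned. Sections 1.1 and 1.4 are background, and no SPECT, PET or stress-echo endpoint follows from them. This stands, and it is why the accuracy point carries less weight. It does not rescue 7.1, which is not background and states a capability outright.

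Three further points also stand in part:

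- Section 5.3 belongs to the study-drug chapter. Its entry follows from every subject receiving EVP1001-1, and it would not exclude non-assigned groups defined by cell exposure. It is supporting evidence only; the main evidence is that no section defines such groups.
- A reader might infer from section 3.1 that no patient will have a scan before cell therapy. The text does not go that far. The procedures flowchart listed in section 14 is not part of the text available, and the Study Summary gives times per exam and about 3 days per patient. What can be said is that section 3.1 describes one sequence and gives no pre- or post-therapy timing.
- Section 4.3 mentions exercise tests and section 8.2 mentions stress before EVP1001-1. Neither specifies stress imaging and section 3.1 schedules none, but these mentions should be reconciled with 3.1.

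**Conclusion.** The point holds. Section 7.1 states a between-arm capability, and a power figure for stem cell engraftment, that the protocol text does not support. Power for an arm comparison is not merely low or high: it cannot be calculated from the documents. The accuracy promise fails for three of its four named comparators, which is a lesser fault of scope.

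Two stronger readings should be resisted. A reader might infer that the trial contains no controlled comparison at all. It does: section 4.3 calls the study baseline-controlled, and sections 3.1 and 7.2 plan EVP1001-1 against gadolinium within the same patients. What is missing is a controlled cell-therapy comparison. A reader might also infer that recipients were all treated elsewhere before entry. Section 4.3 speaks of therapy already received, but sections 1.4 and 2 speak of patients undergoing it, and no section says where it is given.

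The conclusion assumes that the unseen flowchart does not define arms or repeat scans. The power range in the working rests on assumed differences, SDs and shares, and serves only to show how much is left open.

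**What to change.** - **Section 7.1:** delete the sentence on cell-therapy and control arms. Restate the power sentence for the MEMRI versus DEMRI comparison only, remove stem cell engraftment from it, and give the N and the SD of within-patient differences on which it rests.
- **Sections 7.1 and 7.2:** state that any contrast between cell recipients and other patients, and the engraftment correlation, is descriptive or exploratory and non-randomised, and supports no conclusion about a treatment effect.
- **Sections 1.1 and 1.4:** limit the promise of evaluation to the comparisons in sections 3.1 and 3.2, that is, EVP1001-1 against gadolinium MRI with the echo and patient-outcome references. Make no accuracy claim against stress echo, SPECT or PET. Restricting the text to gadolinium alone would contradict section 3.2.

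This is a change of protocol wording and needs no extra patients, scans or data. The downside is that the stated scope becomes narrower.

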### 7.2 Statistical Methods

Student's t-test to compare MEMRI and DEMRI measurement of the infarct and viable myocardium. Pearson's correlation to generate any association between stem cell engraftment/peri-infarct viability and functional restoration and/or clinical outcome.

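### The protocol gives total enrolment as 50, 60 and 120, and the one power statement in Section 7.1 (20% difference, SD 5%, 90% power) justifies none of these figures

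*Combined protocol and SAP*

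**What the plan says.** **Totals.** All of these stand in current text:

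| Total | Where |
|---|---|
| 50 | Study Summary; Section 2 |
| 60 | Section 1.4 (ischemic, non-ischemic and atrial arrhythmia patients); Section 7.3 (ischemic, non-ischemic and atrial cardiomyopathy) |
| 120 | Section 1.1; Section 4.3 (in addition to the 6 pilot patients); Section 8.3.1 |

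Section 7.1 adds an atrial fibrillation cohort: "Accordingly, 60 participants will be needed for the additional cohort".

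**Power.** For a mean difference of 20% in MEMRI signal of engraftment and MEMRI-DEMRI signal of peri-infarct viability, Section 7.1 states: "with a standard deviation of 5%, the t-test sample size calculation in this study has 90% power at the alpha 0.05 significance level". The variances of the two distributions compared are taken to be equal. The section does not say whether the 20% is absolute or relative, whether the 5% belongs to one scan or to the within-patient difference, or whether the test is paired. Earlier in the section, a 9% difference seen in swine is said to allow "delineation of the changes in the peri-infarct viability between the cell therapy and control arms".

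**Design.** Under Section 3.1 each patient is imaged with EVP1001-1 and then with gadolinium, and the two sets of images are compared. Section 5.3, "Method for Assigning Subjects to Treatment Groups", is marked as not applying. Section 7.2 plans a Student's t-test of MEMRI against DEMRI, plus "Pearson's correlation to generate any association between stem cell engraftment/peri-infarct viability and functional restoration".

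**Atrial cohort.** Section 7.1 states: "we expect a difference in DEMRI volume of 40 (+ or - 20) in participants with early disease". For advanced disease the corresponding figure is 60 (± 20). No power level is attached.

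**The concern.** Total sample size determines when enrolment ends and how many people receive an investigational contrast agent. A reader who meets three totals would turn to Section 7.1 to learn which was calculated, and that section does not settle it. The inputs beside the 90% describe a very large standardised effect, for which a handful of patients would do. The wording about two distributions and about arms also fits poorly with a study in which each patient supplies both measurements. If this stays as it is, the precision of the MEMRI-DEMRI comparison at the real sample size is never stated, and neither a review board nor the analyst can tell whether the trial is complete.

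**Working it through.** **Step 1. Can the totals be reconciled?** 60 + 60 (the added atrial cohort) = 120. That leaves the 50 unexplained. It also does not explain the 60 in Sections 1.4 and 7.3, because both of those already include atrial patients.

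**Step 2. Inputs to the power statement (Section 7.1).** Difference 20, SD 5, alpha 0.05, power 90%, t-test. Assumptions added here: two-sided test; both percentages in the same absolute unit. The standardised effect is d = 20/5 = 4.

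**Step 3. Try to reproduce the 90%.** Exact power comes from the noncentral t distribution:
- paired: df = n − 1, noncentrality d√n;
- two groups: df = 2n − 2, noncentrality d√(n/2), with n per group.

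If 5% is a per-scan SD and the two scans are uncorrelated, the SD of the difference is 5√2 = 7.07, and the paired d is 20/7.07 = 2.83.

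| n | Paired, SD of difference 5 | Paired, SD of difference 7.07 | Two groups, n per group |
|---|---|---|---|
| 2 | 34.3% | 24.6% | 56.5% |
| 3 | 90.8% | 70.5% | 94.8% |
| 4 | 99.8% | 95.0% | 99.6% |

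So 90% power is first reached with 3 patients, 4 patients, or 2 × 3 = 6 patients, depending on the reading. At 50, 60 or 120 patients power is effectively 100% on each.

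**Step 4. Work backwards.** For a 20-point difference to have 90% power at the stated totals, the SD must be 20 divided by the standardised effect detectable at that size:

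| Total | Two equal groups | Paired (SD of difference) |
|---|---|---|
| 50 | 20/0.936 = 21.4 | 20/0.468 = 42.8 |
| 60 | 20/0.851 = 23.5 | 20/0.425 = 47.0 |
| 120 | 20/0.597 = 33.5 | 20/0.298 = 67.0 |

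The smallest of these is more than four times the stated 5.

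**Step 5. What a paired statement could look like (illustration only).** Assume the pilot scar values in Sections 1.1 and 1.4, 39±11 for DEMRI and 16±3 for MEMRI in 6 patients, are means and SDs of the quantity to be tested. With within-patient correlation r:

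SD of difference = √(11² + 3² − 2·r·11·3) = √(130 − 66r), which is 11.4 at r = 0 and 8.0 at r = 1.

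Reading ± as an SD agrees with the reported p<0.01. With a difference of 23 in 6 patients, paired p is 0.0043 at r = 0 and 0.0009 at r = 1. If ± were a standard error, p would be 0.100 and 0.035.

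Detectable difference at 90% power = standardised effect × SD of difference:
- 50 patients: 0.468 × 8.0 to 0.468 × 11.4 = 3.7 to 5.3 points
- 60 patients: 0.425 × 8.0 to 0.425 × 11.4 = 3.4 to 4.9 points
- 120 patients: 0.298 × 8.0 to 0.298 × 11.4 = 2.4 to 3.4 points

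**Step 6. Atrial cohort.** If 40 and 60 are early and advanced means, ± 20 is an SD and the 60 patients split equally, then d = 20/20 = 1 and 30 per group gives 96.8% power.

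**The case against.** **The unit is not stated.** If the 20% were relative and the 5% in points, larger numbers follow. For example, 20% of the pilot gap (39 − 16 = 23) is 4.6 points, which needs 26 per group, or 52 in total (90.2%), in an unpaired test. Taking 20% of the MEMRI value of 16 gives 3.2 points, which needs 53 per group, or 106 in total. This stands as a caution: the 3-to-6-patient figures depend on the same-unit reading. It does not rescue the section, which names no base for a relative change and ties the calculation to no total.

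**The 90% may mean at least 90%.** On the same-unit reading, every stated total meets that. A reader might infer from the mismatch that the trial is too small; the figures do not support this.

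**The arms.** A reader might infer that the 90% was calculated for a two-arm trial. The text does not establish that. The arms wording belongs to the swine result, and the two distributions in the power sentence could be MEMRI and DEMRI. Stem-cell recipients may also be recruited, so a non-randomised comparison is possible. What stands is that no such comparison is specified and that the MEMRI-DEMRI test is within-patient.

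**The atrial 60.** It may be tempting to call this a miscalculation. Section 7.1 claims no power for it, and 96.8% on the early-versus-advanced reading is adequate.

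**The printed zero.** Section 7.1 opens with "The total number of 0 patients will power this study adequately". A digit may have been lost in reading the PDF, so this is not counted as an error.

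**Conclusion.** The point holds in two parts. First, the three totals are incompatible in current text; this rests on no assumption. Second, the only power statement justifies none of them. With 20% and 5% in the same absolute unit and a two-sided test, it calls for 3, 4 or 6 patients against stated totals of 50 to 120.

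The MEMRI-DEMRI comparison needs the SD of the paired difference, which the plan does not identify. The pilot-based figures show only the order of magnitude: scar volume may not be the quantity to which the 5% refers.

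This should be corrected before the plan is relied on, chiefly because of the conflicting totals.

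**What to change.** - State one total with its ventricular/atrial split, and use it in the Study Summary and Sections 1.1, 1.4, 2, 4.3, 7.1, 7.3 and 8.3.1. Which total is intended is for the sponsor to say.
- In Section 7.1, replace the 90% statement with paired power, or the detectable difference, at that total. Give the unit of the effect (absolute or relative), the SD of the within-patient difference and its source. If the pilot SDs are judged to apply, the ranges in Step 5 are a starting point.
- Remove the wording about cell-therapy and control arms, or identify it as a non-randomised comparison with its own sample-size basis.
- For the atrial cohort, say which comparison the 40 ± 20 and 60 ± 20 describe, and give the power of 60 patients for it.

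Cost: a rewrite of Section 7.1 and alignment of one number in the other sections. Correcting the power statement does not itself call for more patients, visits or scans. Whether planned enrolment changes depends on which total the sponsor confirms.

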#### Parameters to be Measured:

A standard physical assessment will be performed on the day of imaging (approximately 1-hour post dosing). Body temperature and respiration rate will be measured within 24 hours prior to dosing and at approximately 1- and 2-hours post dose. A standard 12-lead EKG will be performed both before and after the MR study to assure no significant EKG changes have occurred. Patient's hemodynamics will also be serially monitored. A baseline BP and HR will be performed before beginning the study. After EVP1001-1 contrast infusion, BP and HR will be measured every 2 minutes until 10 minutes post EVP1001-1 contrast infusion after which point a BP and HR will be measured every 5 minutes until the conclusion of the MEMRI and every 10 minutes until the conclusion of DEMRI study. There will be a 5-minute post administration observation interval outside the scanner. The patient will also have continuous EKG monitoring during this time. After the study, the patient will have another standard 12-lead EKG performed to compare with the pre-MRI 12-lead EKG. The patient's symptoms will be

CONFIDENTIAL

This material is the property of Stanford University. Do not disclose or use except as authorized in writing by the study sponsor

reassessed 1 hour after infusion of the EVP1001-1 contrast. A differential and serum chemistry profile (with liver function test) will be performed within a month prior to administration of EVP1001-1 and within 24 hours post EVP1001-1. Adverse events (AEs) and discomforts will be recorded until discharge from the imaging center. At the 24 hour follow-up, the subject will be evaluated by telephone to determine if any AEs occurred from the time the subject left the imaging center. The subjects will have a contact number to report any AEs or to ask questions. Any clinically relevant changes from baseline in vital signs, ECG rhythm, clinical chemistries or physical condition and all AEs will be followed until resolution or until the outcome is known. Injection-associated discomforts will be recorded during administration and until imaging is completed. Primary efficacy will be based on determining whether the heart is normal or abnormal and if abnormal whether there is an infarction, ischemia or both. This provides the basis for calculating sensitivity, specificity, accuracy and predictive values. In addition, the location, size, conspicuity and associated confidence for any disease will be recorded.

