### 7.3 Subject Population(s) for Analysis

We expect to enroll 60 patients with various cardiomyopathies including NICM, ICM, and ACM (dilated cardiomyopathy, ischemic cardiomyopathy, and atrial cardiomyopathy). Our goal is to demonstrate improved sensitivity and specificity of identifying viable myocardium and PIR in the ventricles and atria in various cardiac patients to help improve clinical management

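### The only power statement covers a t-test on a mean signal difference; the sensitivity and specificity goal has no sample-size basis and no analysis that could show an improvement

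*Combined protocol and SAP*

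**What the plan says.** All references are to the combined protocol and SAP.

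- **Power (7.1).** The plan states that "the t-test sample size calculation in this study has 90% power at the alpha 0.05 significance level". The effect behind this is a 20% mean difference, named both for the MEMRI signal of engrafted stem cells and for the MEMRI-DEMRI signal of viability around the infarct. The SD is set at 5% and the variances are taken as equal. The direction of the test (one- or two-sided) is not given.
- **Primary efficacy (3.1, Parameters to be Measured).** Each heart is read as normal or not and, if not, as infarct, ischemia or both. Of this reading the plan says: "This provides the basis for calculating sensitivity, specificity, accuracy and predictive values". Section 3.2 also judges efficacy on whether infarct or ischemia is present, relative to echo and gadolinium-based MRI and with a comparison to patient outcomes.
- **Goal (7.3).** "Our goal is to demonstrate improved sensitivity and specificity of identifying viable myocardium and PIR", in the ventricles and atria. No comparator and no size of improvement are named.
- **Analysis (7.2).** "Student's t-test to compare MEMRI and DEMRI measurement of the infarct and viable myocardium", plus a Pearson correlation. The Study Summary lists the same two methods. Neither place gives a method for a proportion.
- **Planned size.** 50 (Study Summary, Section 2), 60 (1.4, 7.3) or 120 (1.1, 4.3, 8.3.1).

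**The concern.** Sensitivity and specificity are proportions. Each is estimated only in the patients whom the reference calls diseased or not diseased. Every patient has both scans, so a gain of one technique over the other is a paired comparison of proportions. A t-test calculation on a continuous signal carries no information about the power of that comparison.

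The planned test has the same gap. A significant mean difference shows that the two techniques measure different amounts of scar, and this can coexist with no gain in accuracy, or with a loss. The six-patient pilot illustrates it. Section 1.1 reports scar of 39% by DEMRI and 16% by MEMRI (p<0.01) and reads this as over-estimation by DEMRI, but the two figures alone do not show which is closer to the truth.

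Followed as written, the trial would present a near-certain t-test as its adequately powered efficacy result, while the goal in 7.3 has no test. An imprecise accuracy estimate could then be read against a 90% figure that was never computed for it.

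**Working it through.** **1. The plan's own figure.** Inputs from 7.1: difference 20, SD 5, alpha 0.05 (taken as two-sided). The standardised effect is 20/5 = 4. Power comes from the noncentral t distribution.

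- Paired form, taking 5 as the SD of the differences: noncentrality 4 × √n. With n = 3 this is 6.93 on 2 degrees of freedom, and power is 90.8%.
- Two-sample form: noncentrality 4 × √(n/2) with n per group. With n = 3 per group this is 4.90 on 4 degrees of freedom, and power is 94.8%.
- At 50, 60 or 120 patients, power is essentially 100% in either form.

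The stated 90% is reached at about three patients and is not reproduced at any planned size. For 90% power at a difference of 20 in the two-sample form, the SD would have to be about 21 (N = 50), 23 (N = 60) or 34 (N = 120).

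**2. The accuracy goal.** The documents give no rates, agreement between reads or prevalence, so what follows is an assumed range. The test is the exact two-sided McNemar test at 0.05, at patient level, with m patients evaluable for the measure. The agreement assumptions are:

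- *Independent reads.* For 80% to 90%, the new technique alone is right in 0.20 × 0.90 = 0.18 and the old alone in 0.80 × 0.10 = 0.08. For 70% to 90%, these are 0.30 × 0.90 = 0.27 and 0.70 × 0.10 = 0.07.
- *Maximum agreement.* Every change is a gain, so the discordant count is Binomial(m, gain). With k discordant pairs all in one direction, p = 2 × 0.5^k. This is 0.0625 at k = 5 and 0.031 at k = 6, so power is P(count ≥ 6).

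| Evaluable m | 80% to 90%: independent | 80% to 90%: maximum agreement | 70% to 90%: independent | 70% to 90%: maximum agreement |
|---|---|---|---|---|
| 25 | 7% | 3% | 28% | 38% |
| 30 | 10% | 7% | 36% | 57% |
| 50 | 20% | 38% | 63% | 95% |
| 60 | 25% | 56% | 73% | 99% |
| 120 | 51% | 98% | 97% | 100% |

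Patients needed per measure for 90% power: 91 to 282 for 80% to 90%, and 45 to 91 for 70% to 90%.

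**3. Precision.** Clopper-Pearson 95% limits for an observed 80%: 24/30 gives 61% to 92%, and 40/50 gives 66% to 90%.

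**The case against.** The strongest reply is that 7.1 ties its 90% to a t-test by name and never assigns it to sensitivity or specificity. That t-test matches 7.2, the Study Summary and Specific Aim 1, which only sets out to characterize injury. Section 3.1 says that accuracy measures will be calculated, which is estimation. In a single-center, open-label phase 2 study, leaving accuracy unpowered is a common choice. This stands, and it limits the harm. It does not remove the sentence in 3.1 that makes the classification primary, or the goal in 7.3 of showing an improvement.

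A reader might infer that power for the accuracy goal is far below 90% at the planned sizes. The documents do not support that as a fact. The table runs from about 3% to nearly 100%, and low values for both measures jointly would need a split of diseased and non-diseased patients that no section gives. Section 7.3 concerns viable myocardium and the peri-infarct region, while 3.1 concerns infarct and ischemia. The unit of analysis for 7.3 is not stated either, so the patient-level figures are only indicative.

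A second objection concerns the remedy and also stands. Section 3.2 puts gadolinium MRI in the reference standard, and DEMRI is the gadolinium scan. To the extent that it sets the reference, DEMRI is right by definition and MEMRI disagreements count as errors. A paired accuracy test against that reference is not valid, and the calculations in step 2 presuppose a different one.

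**Conclusion.** The point holds as a mismatch within the plan. The only power calculation and the only planned tests concern a mean difference and a correlation, while primary efficacy and the stated goal concern diagnostic accuracy. None of this rests on assumed figures.

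Power for the accuracy goal is not established; it cannot be called low without inputs that the documents lack. Assuming a 10-point gain from 80%, it stays well short of 90% with 50 or 60 evaluable patients. A 20-point gain from 70%, or 120 evaluable patients, can exceed 90% if agreement between reads is high. These figures assume patient-level reads, a two-sided exact test and a reference independent of DEMRI.

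Separately, the 90% does not follow from the inputs in 7.1 at any planned size. The section speaks of cell therapy and control arms as well as of MEMRI against DEMRI, so the contrast being powered is itself unclear.

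**What to change.** 1. **7.1.** State that the calculation covers only the mean-difference t-test and that no power is claimed for accuracy measures. Do not keep 90% for that t-test; name the contrast and the N, and recompute. For accuracy measures, give the expected exact 95% confidence interval at the planned size, as in step 3 of the working.
2. **7.3.** Replace the aim of demonstrating an improvement with that of estimating sensitivity and specificity.
3. **7.2.** Add exact binomial 95% confidence intervals for the accuracy measures, and say that improved accuracy will not be inferred from the t-test. Compare MEMRI with DEMRI accuracy (McNemar's test with a confidence interval for the paired difference) only against a reference that excludes gadolinium MRI, such as patient outcomes. Otherwise report only MEMRI's agreement with the reference.

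The cost is wording in 7.1 to 7.3 and a few lines of analysis code, with no extra patients, scans or readers. If the paired comparison is wanted, a decision on the reference standard is also needed. The downside is that the trial can no longer imply adequate power for its accuracy goal.
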